Eligibility criteria	10	Inclusion and exclusion criteria for participants. If applicable, eligibility criteria for study centres and individuals who will perform the interventions (eg, surgeons, psychotherapists)	SP, 7
Interventions	11a	Interventions for each group with sufficient detail to allow replication, including how and when they will be administered	SP, 8
	11b	Criteria for discontinuing or modifying allocated interventions for a given trial participant (eg, drug dose change in response to harms, participant request, or improving/worsening disease)	SP, 10
	11c	Strategies to improve adherence to intervention protocols, and any procedures for monitoring adherence (eg, drug tablet return, laboratory tests)	SP, 10
	11d	Relevant concomitant care and interventions that are permitted or prohibited during the trial	SP, 10
Outcomes	12	Primary, secondary, and other outcomes, including the specific measurement variable (eg, systolic blood pressure), analysis metric (eg, change from baseline, final value, time to event), method of aggregation (eg, median, proportion), and time point for each outcome. Explanation of the clinical relevance of chosen efficacy and harm outcomes is strongly recommended	SP, 12
Participant timeline	13	Time schedule of enrolment, interventions (including any run-ins and washouts), assessments, and visits for participants. A schematic diagram is highly recommended (see Figure)	SP, 12
Sample size	14	Estimated number of participants needed to achieve study objectives and how it was determined, including clinical and statistical assumptions supporting any sample size calculations	SP, 13

Recruitment	15	Strategies for achieving adequate participant enrolment to reach target sample size	SP, 13
-------------	----	---	--------

Methods: Assignment of interventions (for controlled trials)

Allocation:

Sequence generation	16a	Method of generating the allocation sequence (eg, computer-generated random numbers), and list of any factors for stratification. To reduce predictability of a random sequence, details of any planned restriction (eg, blocking) should be provided in a separate document that is unavailable to those who enrol participants or assign interventions	SP, 14
Allocation concealment mechanism	16b	Mechanism of implementing the allocation sequence (eg, central telephone; sequentially numbered, opaque, sealed envelopes), describing any steps to conceal the sequence until interventions are assigned	SP, 14

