Our study coordinator, study physicians, physical therapists, PI ([name]), and research collaborators recruited subjects using a variety of strategies shown effective in the past. First, the team identified potential subjects using Institutional Review Board (IRB) approved resources to inform persons with SCI that are currently admitted to inpatient rehabilitation/outpatient units of Spaulding Rehabilitation Hospital, Boston University Medical Center, Massachusetts General Hospital, Gaylord hospital, Albany Medical Center, and Maine Medical Center. Subjects also will be recruited by word of mouth and flyers at these facilities. Eligible subjects screened at INSPIRE Laboratory, Spaulding Rehabilitation Hospital Cambridge, MA. At the screening visit, subjects informed of this project, their potential involvement, the possible benefits, and risks, and their right to terminate participation at any time without penalty. Qualifying subjects in agreement with the study details asked to sign the informed consent and HIPAA form approved by Partners IRB. All potential subjects entered the study according to the inclusion/exclusion criteria above and following medical clearance. Experiments will be conducted at the Spaulding Rehabilitation Hospitals.

11. Interventions

- a. Intervention Procedures: This placebo-controlled study will examine the combined effects of caffeine (vs. placebo) and AIH (vs. SHAM) on walking performance in persons with chronic, iSCI. Participants will receive three combinatorial interventions in random order: placebo+AIH, caffeine+AIH, caffeine+SHAM. The order of interventions will be block randomized. The initial screening and evaluation procedures are similar for all participants. For each intervention, participants will complete up to 8 visits/intervention (1 baseline/intervention + 5 treatment days/intervention + 2 follow-up days/intervention). Participants will complete a total of 24 visits (8 visits/intervention x 3 interventions) after the initial screen. Participant enrollment and allocation will be completed during the screening visit. Baseline will be recorded up to 3 days prior to the first intervention.

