Participants will be randomized to a sequence of three interventions (Table 1). Participants will participate in a single-day screening and 24 visits (1 baseline/intervention + 5 treatment days/intervention + 2 follow-up days/intervention). Participant enrollment and allocation will be completed during the screening visit. Baseline visits will occur up to 3 days prior to the first treatment. A two-week washout will follow the last treatment day. This washout duration is more conservative than washout durations reported in previous animal and human intermittent hypoxia studies.^{53, 54}

DETAILED STUDY PROTOCOL

Table 1. Timing Schedule for enrollment, interventions, and assessments

Timepoints (days)	Enrollment		Baseline			Intervention			Follow-ups/Washout	
	-5	0	1	2	3	4	5	8	14	
Screening and Allocation Timing										
Eligibility screen	x									
Informed consent	x									
Medical clearance	x									
Allocation		x								
Drug script		x								
Intervention Timing										
Placebo+AIH			x	x	x	x	x			
Caffeine+AIH			x	x	x	x	x			
Caffeine+SHAM			x	x	x	x	x			
Assessment Timing										
Primary outcome										
• Walking speed (10MWT, s)		x					x	x	x	
Other outcomes										
• Voluntary leg strength		x					x	x	x	
• Spasticity		x					x	x	x	
• Spasm frequency		x					x	x	x	
• Walking function		x					x	x	x	
• Walking distance (6MWT, m)		x					x	x	x	
• Walking Balance (TUG, s)		x					x	x	x	
• Blinding Questionnaire			x	x	x	x	x			
• Weight (kg)		x						x	x	
Safety Outcomes										
• Pain (0-10)		x	x	x	x	x	x	x	x	
• Blood pressure (mmHg)		x	x	x	x	x	x	x	x	
• Heart rate (BPM)		x	x	x	x	x	x	x	x	
• Oxygen saturation (%)		x	x	x	x	x	x	x	x	
• Memory (0-30)		x	x	x	x	x	x	x	x	
Biomarkers										
• CYP1A2 Polymorphism		x								
• Caffeine serum level (mg/L)			x				x			
• Inflammation (CRP)			x				x			

DETAILED STUDY PROTOCOL

14. Sample size

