Eligible participants will be screened at the designated site facilities (i.e., INSPIRE Laboratory, Spaulding Rehabilitation Hospital at Boston and at Cambridge sites). At the screening visit, subjects will be informed of this project, their potential involvement, the possible benefits and risks, and their right to terminate participation at any time without penalty. Qualifying subjects in agreement with the study details will be asked to sign the informed consent and HIPAA form approved by Spaulding Rehabilitation Hospital's IRB. All potential subjects will enter the study according to the inclusion/exclusion criteria above and following medical clearance. Experiments will be conducted at the Spaulding Hospital in Cambridge.

Prospective subjects will be contacted by telephone, mail or email and briefly informed of the methods, inclusion criteria, and purpose of the study. We also will provide a description of this study on <http://www.ClinicalTrials.gov>, as required by U.S. law. In all cases, recruitment will not be coercive, will not involve undue inducements, and will accurately reflect the study.

We will recruit individuals who reflect the population of persons with SCI in the Northeast region of the United States, which is 19% women, 81% men, 67% Caucasian, 24% African American, 8% Hispanic, 2% Asian, and 1% Native American. We do not yet know of any differences in responsiveness to AIH or caffeine according to the gender or race of persons with SCI.

Children will not be included in this study. The proposed research is aimed at understanding the plasticity-inducing mechanisms of caffeine and repetitive acute intermittent hypoxia exposure in adults with chronic, incomplete spinal cord injury. A separate study would be required to address the confounding effects of childhood growth and development after spinal injury on the proposed intervention study – a topic best suited for future research once the underlying mechanisms of the intervention are better characterized.

16. Assignment of interventions (for controlled trials)

Assignment of interventions for study participants will be done using allocation sequence generation, concealment, and double-blinded implementation.

- Allocation sequence generation – This study will consist of three blocks: caffeine+AIH, caffeine+SHAM, and placebo+AIH. We will generate the blocked randomization for the study participants using a random number list randomizer (Random.org).⁵⁵ Participants will

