DETAILED STUDY PROTOCOL

randomly receive each intervention block with a minimum of 2-week wash-out between blocks. We will analyze *post hoc* differences in age, impairment score, assistive device used, baseline lower extremity motor scores, and male-female ratio using independent t-tests.

- Concealment mechanism – We will conceal the intervention allocation from the evaluators performing the assessments, treatment administrators, and the study participant.
- Implementation – The PI and biostatistician will generate the allocation sequences for the cross-over study. The trial coordinator will enroll participants and study staff who are not training or assessing the participants will assign the block randomized interventions.

17. Blinding (masking)

The PI, participants, care provider, and clinical evaluators will be made aware of possible air mixtures and caffeine interventions, but not made aware of the combinatorial intervention delivered. Based upon reports from participants (N=6) blinded during our prior study,³³ 4 of 6 guessed incorrectly or were uncertain of the intervention received, suggesting our prior blinding were effective.

18. Data collection, management, and analysis

Data collection methods

- Assessment and collection plans: Physical evaluations will be completed by the study's licensed physical therapists or occupational therapists and/or trained research study staff. Functional ability of subjects will be evaluated using standard clinical assessments with high inter-rater reliability: American Spinal Injury Association Impairment Scale (AIS) lower extremity motor scores (LEMS) to quantify strength,⁵⁶ and Spinal Cord Assessment Tool for Spastic Reflexes (SCATS), and the Penn Spasm Frequency Scale (PSFS) which is a self-report assessment of the frequency and severity of muscle spasms⁵⁷ and modified Ashworth Scale to quantify spasticity.⁵⁸ We also will record pain severity using the well-established Wong-Baker FACES scale, which shows high test-retest reliability and interpretability as well as good content and construct validity.^{59, 60} Clinical ratings of walking ability, including Walking Index for Spinal Cord Injury (WISCI) II⁶¹ and/or SCI Functional Ambulation Index (SCI-FAI),⁶² will be assessed based on video recordings of the 10MWT.

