The main objective of this clinical trial is to evaluate the effects of a common, safe adenosine A_{2A} antagonist, caffeine, on recovery of walking following dAIH in persons with chronic iSCI. While highly specific A_{2A} receptor antagonists, such as MXS-3 and ZM2412385, block cross-talk in rats,¹⁷ their safety in SCI is not known. On the other hand, caffeine offers the ideal blend of known

safety, metabolism, and efficacious A_{2A} receptor antagonism.¹⁸ Even at low plasma concentrations (1-10µM) after one cup of coffee, caffeine antagonizes A_{2A} receptors,¹⁸ and the efficacy of moderate caffeine in blocking neural A_{2A} receptors is illustrated by the neuroprotective effects of regular caffeine consumption in dopaminergic transmission in Parkinson's Disease.¹⁹ Although caffeine has many neurobiological actions, caffeine's actions at physiologically relevant doses (1-100 µM), including the proposed dose of up to 6 mg/kg body weight, are mediated by adenosine receptor antagonism versus phosphodiesterase inhibition, release of intracellular calcium stores, or other site.²⁰ Our study will quantify the daily (5 consecutive days) effects of caffeine (e.g., 4 mg/kg) as an adjunctive therapy to dAIH for restoring walking function in persons with chronic iSCI. This dose has known safety in iSCI and substantial antagonism to A_{2A} receptors.^{18, 21, 22}

III. Methods: Participants, interventions, and outcomes

9. Trial Design

We will conduct a placebo-controlled, cross-over, block-randomized intervention study to assess the efficacy of daily caffeine prior to AIH on improving walking function in persons with chronic, motor-incomplete SCI.

10. Randomization

Assignment of interventions for study participants will be done using allocation sequence generation, concealment, and double-blinded implementation.

- Allocation sequence generation – This study will consist of three blocks: caffeine+AIH, caffeine+SHAM, and placebo+AIH. We will generate the blocked randomization for the study participants using a random number list randomizer (Random.org).²³ Participants will randomly receive each intervention block with a minimum of 2-week wash-out between blocks. We will analyze *post hoc* differences in age, impairment score, assistive device used, baseline lower extremity motor scores, and male-female ratio using independent t-tests.

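### No balance of the six intervention orders is specified across the 20 people, and the primary model has no round term, so a trend by round in the size of the 10MWT change would cost precision

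*Combined protocol and SAP*

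**What the plan says.** - Protocol section 16, repeated in SAP section 10, defines the blocks as the interventions: "This study will consist of three blocks: caffeine+AIH, caffeine+SHAM, and placebo+AIH". Participants then "randomly receive each intervention block with a minimum of 2-week wash-out between blocks", so a block here is a treatment round.
- The same sections give the tool: "We will generate the blocked randomization for the study participants using a random number list randomizer". No block size, list of orders or balance rule follows.
- Elsewhere the wording is general. Protocol section 11 says "The order of interventions will be block randomized". Section 13 says "Participants will be randomized to a sequence of three interventions". Section 16 adds "The PI and biostatistician will generate the allocation sequences for the cross-over study".
- The primary model (protocol section 20, SAP section 27) lists intervention and day as fixed effects and subject as random. Round and sequence do not appear.
- SAP section 26 defines the primary outcome as change in 10MWT from baseline, and each intervention has its own baseline visit. It also plans to compare baselines between interventions as a check on washout. SAP section 27 moves to ANCOVA if they differ.

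**The concern.** Three interventions can be given in six orders. In a crossover, balancing the orders over participants or fitting a term for round keeps a time trend out of the treatment comparison. This plan specifies neither. Each person has three rounds and 24 visits after screening, so the response to a week of treatment could well shrink or grow from round to round, for example through a ceiling or carry-over. If one intervention happens to fall later than another on average, part of that trend appears in their difference. What is at stake is the precision of caffeine+AIH versus placebo+AIH in a trial of 20 people.

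**Working it through.** The documents give no figure for balance of orders, so there is none to reproduce.

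**Inputs**
- N = 20, including 17% attrition (protocol section 14, SAP section 11). 20 × 0.83 = 16.6, so 16 completers is used as the second case.
- SD 1.3 s, the pooled SD in the same sections. I take it as the residual SD of one change score. The documents do not say whether it refers to a change or to a single time, so this is an assumption.
- Trend b in the change score, in seconds per round. The documents give none. I use 0, 0.3, 0.65 and 1.3 as assumptions.
- Each person's order is drawn independently from the six. This is also an assumption.

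**Chance imbalance**

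1. For one person, the position of intervention A minus that of B takes the values −2, −1, −1, 1, 1, 2 over the six orders. The mean is 0 and the variance is (4 + 1 + 1 + 1 + 1 + 4)/6 = 2.
2. The mean over n people has SD √(2/n): √(2/20) = 0.32 rounds and √(2/16) = 0.35 rounds.
3. At n = 20 the absolute difference is 0.5 rounds or more in about 13% of trials, and its 95th percentile is 0.60 rounds (simulation).
4. At least one of the six orders is unused in 15% of trials at n = 20 and 30% at n = 16.

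**Effect on the contrast at n = 20**

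Without a round term, SE = √(2 × 1.3²/n + b² × 2/n). The first part is 2 × 1.69/20 = 0.169.

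| Trend b (s per round) | Added variance b² × 0.1 | SE without round term (s) | Shift at an imbalance of 0.60 rounds (s) |
|---|---|---|---|
| 0 | 0 | √0.169 = 0.41 | 0 |
| 0.3 | 0.009 | √0.178 = 0.42 | 0.18 |
| 0.65 | 0.042 | √0.211 = 0.46 | 0.39 |
| 1.3 | 0.169 | √0.338 = 0.58 | 0.78 |

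Simulation gave the same standard errors: 0.41, 0.42, 0.45 and 0.58 s. With round in the model the SE stayed at about 0.42 s whatever the trend.

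**Test size.** With independent orders and no round term, the size of the 5% test was 4.6% to 5.2% over these trends. The average imbalance is zero, and the trend enters the residual variance as well as the contrast.

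**Permuted blocks of the six orders.** The SD of the position difference falls to 0.09 rounds with all 20 completing and to about 0.18 with 16 completers. Without a round term, the balanced design gave a test size of about 0.8% at 1.3 s per round, because the trend stays in the residual variance but has nearly left the contrast. With a round term the size was about 5%.

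**The case against.** Four points can be made for the plan.

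1. A reader might infer that each person's order is shuffled separately and that the orders are therefore unbalanced. The documents do not say so. Randomization to a sequence, with sequences generated by the PI and biostatistician, also fits a pre-generated list with balanced orders. The SPIRIT checklist reproduced in the supplement says of item 16a that "details of any planned restriction (eg, blocking) should be provided in a separate document", so silence in the protocol does not show that no restriction exists. The enrollment flowchart could not be seen either. This stands: the point is that balance is not specified, not that it is absent.
2. A reader might infer that any practice or fatigue effect loads onto one intervention. That goes too far. A shift that moves a whole round up or down cancels in the change from that round's own baseline. Only a trend in the size of the change matters. This stands for the outcome as SAP section 26 defines it. The planned baseline comparison and ANCOVA concern baseline level and do not adjust for a trend in the change.
3. Random orders are balanced in expectation, so there is no systematic bias and type I error is held. This also stands.
4. The example trend is large. At 1.3 s per round, rounds 1 and 3 differ by 2.6 s, which exceeds the 2.4 s change in the preliminary study. At 0.3 s per round the loss is slight: 0.42 against 0.41 s.

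What remains is the missing round term. Nothing else in the stated analysis does its work. Once round is modelled, redrawing the list improves the SE by only about 2%.

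**Conclusion.** The concern holds as a gap in specification with a limited cost. The plan calls the interventions blocks, gives no rule that balances the six orders, and fits no round term. Under independent orders, a trend by round in the size of the change adds chance error that the analysis leaves unadjusted. At N = 20 the SE rises from about 0.41 s to between 0.42 s (trend 0.3 s per round) and 0.58 s (1.3 s per round). These figures rest on independent drawing, a residual SD of 1.3 s for the change, and a linear trend whose size is assumed. The documents do not support a claim of known imbalance, systematic bias or excess false positives. This is a worthwhile improvement and not a flaw that invalidates the trial. The modelling change matters more than the list.

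**What to change.** - Add round (first, second, third) as a fixed effect in the primary mixed model in protocol section 20 and SAP section 27. It costs 2 degrees of freedom and about 1–3% in SE if there is no trend.
- State in protocol section 16 and SAP section 10 how the orders are generated, or refer to the restricted document that holds this. Report the number of people given each order.
- If the list has not been drawn, draw it as permuted blocks of the six orders: three full blocks (18 people) plus two orders from a fourth. Exact balance is impossible at 20, since 20 is not a multiple of 6; the best available split is 4/4/3/3/3/3. The cost is a different list, with N and visits unchanged.
- Do not balance the orders without the round term, because the test becomes conservative when a trend exists. If the list already exists, the round term alone recovers nearly all of the precision.

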We will quantify overground walking ability using the 10MWT.⁴⁹ Subjects will perform 2 trials each of the 10MWT at their fastest but safe speed with a minimum of 1-minute rest between trials. Average speed across the two 10MWT trials will be used for analyses. The validated assessment tool will provide an indication of return of our subject population to pre-morbid activities following the initial neurological insult. The 10MWT has high inter-rater reliability, and the rating procedure can be accomplished in approximately 30 minutes.

The screening and physical assessment procedures will last approximately 1.5 hours.

To ensure safety, we also will assess pain, spasticity, systemic hypertension, and autonomic dysreflexia prior to and following caffeine and AIH interventions. We routinely measure pain, spasticity, and incidence of hypertension and autonomic dysreflexia as part of our study protocols in persons with chronic SCI.^{32, 33} We will make measurements at baseline, after session 5, and one-week follow-up, and again at two-weeks follow-ups.

Quantify pain: We will assess pain severity using the Wong-Baker FACES scale of 0 (no pain) to 5 (extreme pain).^{59, 60}

DETAILED STUDY PROTOCOL

Quantify spasticity: We will assess spasticity using the Spinal Cord Assessment Tool for Spastic Reflexes (SCATS).⁵⁸ We will quantify total lower extremity spasticity score using the cumulative sum of 3 SCATS subscales: clonus (0=no spasticity; 3=severe), flexor (0=no spasticity; 3=severe), and extensor (0=no spasticity; 3=severe).

Quantify systemic hypertension incidence rate: In addition to monitoring during the intervention, we will measure systolic and diastolic BP at baseline, after sessions 5, and again at follow-ups. We will define a systemic hypertensive event as a systolic pressure exceeding 140 mmHg and/or diastolic pressure exceeding 90 mmHg.^{46, 47}

We will compute hypertension incident rate for each intervention group as the number of hypertensive events divided by the total person-time. We define person-time in units of person-measures (the sum of the total number of BP measurements) taken for each person. Person-measures accounts for the total number of chances for detecting a hypertensive event and accounts for measurements not made due to drop-out or a disqualifying adverse event.⁶³ Finally, we will compute Relative Risk for each Aim as the incidence rate in the dAIH groups over the incidence rate in the dSHAM groups.⁶⁴

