Quantify autonomic dysreflexia incidence rate: We will assess the occurrence of autonomic dysreflexia in all intervention groups. Systolic blood pressure (SBP) will be measured as detailed in common methods. We will assess SBP at baseline, and before, during and immediately after breathing interventions, and again at follow-ups. Additional SBP measurements will be made if participants first present with symptoms characteristic of autonomic dysreflexia (e.g., headache, diaphoresis, blurred vision). An autonomic dysreflexia event will constitute a participant having a SBP increase from baseline of 20 mmHg or SBP greater than 150 mmHg with complaints of headache, diaphoresis, and/or blurred vision and will be diagnosed by our study team clinicians (physicians and physical therapists). An autonomic dysreflexia event will result in termination of study participation and require prompt evaluation by the team physicians and emergency medical team.

We will compute autonomic dysreflexia incident rate for each group as the number of autonomic dysreflexia events divided by the total person-time. We define person-time in units of person-days (the number of days a person remains in the study). Person-days accounts for the total number of chances for detecting autonomic dysreflexia and accounts for days on which measurements were not made due to drop-out or a disqualifying adverse event.⁶³ Finally, we will compute Relative Risk as the ratio of incidence rates between groups.⁶⁴

We previously demonstrated that daily exposures of AIH (up to 5 consecutive days) do not elicit adverse clinical events in persons with chronic SCI.^{32, 33} Similarly, rodents exposed to daily exposure for 7 consecutive days did not induce hippocampal cell death, changes in body mass, or hypertension,^{8, 9} including in animals early after injury.⁸ Determining whether dAIH or in combination protocols lead to the onset of significant pathology (pain, spasms, hypertension, autonomic dysreflexia) in persons with SCI is essential for establishing safe delivery of caffeine combined with AIH in this earlier stage of injury.

Quantify inflammation: We will quantify inflammation using measures of C-reactive protein concentrations in the blood.

- Participant retention plans: Whether or not you complete the whole study, we will pay you \$25 for each visit you do complete. We will also reimburse for up to \$100 per visit in travel

DETAILED STUDY PROTOCOL

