All data will be managed using REDCap⁶⁵, MS 365 Excel 16.54 (Microsoft, USA), and MATLAB R2020a (Mathworks Inc, USA) and will be analyzed using SPSS[®] Statistics 26 (64-bit edition, IBM, USA). Descriptive statistics, including means, standard deviations and 95% confidence intervals of the within-participant pre-post change for each intervention will be calculated for all measures. The baseline characteristics of the participants will be compared using parametric and non-parametric inferencing.

Hypothesis testing: To evaluate our main hypothesis that caffeine prior to AIH enhances walking recovery, we will perform a linear mixed model with fixed effects at a significance at the p=0.05 level.⁶⁶ Intervention (caffeine+dAIH, caffeine+SHAM, placebo+dAIH) and time (day) will be the fixed main effects, with subject as random effect and walking speed (10MWT) as repeat measures. Differences from BL will be compared between and within interventions at D₅, F₁, and F₂. Bonferroni corrections will be made for multiple comparisons. If distributions are not normal, we will perform comparable nonparametric tests. If baseline measures are significantly different between sessions (interventions), an analysis of co-variance (ANCOVA) will be used to analyze the data. We predict walking speed (10MWT) will be greater after daily caffeine+AIH as compared to after daily placebo+AIH and daily caffeine+SHAM.

Blinding integrity analysis: we plan to rigorously quantify blinding integrity here. We will ask participants and raters to guess the intervention received at the end of each intervention and indicate guess confidence using a Likert scale.^{67,68} We will use a contingency table and Fischer's

DETAILED STUDY PROTOCOL

Exact Test to determine if the probability of correct guessing is different from chance. Using multivariate logistic regressions, we also will assess factors that may influence guessing (i.e., adverse events, perceived effects, and sensorimotor changes). In the event of a medical emergency, we will unblind the PI, study participants, and care provider. We also will notify IRB of treatment allocation during adverse event reporting as necessary.

V. Monitoring

21. Data monitoring

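### Interventions are compared on blood pressure only through event rates; no within-person contrast in mmHg is specified, and the 140/90 ratio does not isolate caffeine

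*Combined protocol and SAP*

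**What the plan says.** Protocol 18 (Quantify systemic hypertension incidence rate) sets the event: "We will define a systemic hypertensive event as a systolic pressure exceeding 140 mmHg and/or diastolic pressure exceeding 90 mmHg". Besides monitoring during the intervention, "we will measure systolic and diastolic BP at baseline, after sessions 5, and again at follow-ups". The summary is a rate: "We will compute hypertension incident rate for each intervention group as the number of hypertensive events divided by the total person-time", where person-time is the number of BP readings taken. The comparison is a ratio: "we will compute Relative Risk for each Aim as the incidence rate in the dAIH groups over the incidence rate in the dSHAM groups".

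The next paragraph of Protocol 18 defines autonomic dysreflexia as "SBP increase from baseline of 20 mmHg or SBP greater than 150 mmHg" with symptoms and a diagnosis by study clinicians. It compares incidence rates between groups by a ratio, without naming the groups. It also states the aim: "Determining whether dAIH or in combination protocols lead to the onset of significant pathology (pain, spasms, hypertension, autonomic dysreflexia) in persons with SCI is essential".

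BP is available on its own scale. Table 1 of the protocol lists it in mmHg at baseline, on each of the five treatment days and at both follow-ups. Protocol 11a (Breathing intervention) adds a reading at every fifth breathing interval, at the start and end of walking practice, and at session end.

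Protocol 20 and SAP 27 promise "means, standard deviations and 95% confidence intervals of the within-participant pre-post change for each intervention" for all measures. The linear mixed model in both sections names the 10MWT only. The SAP uses 140/90 only in its stopping text (SAP 13), and SAP 29 anticipates no further analyses.

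**The concern.** Two things are lost.

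The first is sensitivity. Protocol 10 excludes people with hypertension, so most readings should start below 140/90. A rise that stays under the cut adds no events and leaves the ratio where it was. The crossover gives each person's pressure under all three conditions, and a pooled ratio of event rates does not use that pairing. If the comparison condition has few or no events, the ratio is erratic or cannot be computed.

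The second is the contrast itself. The three conditions are caffeine+AIH, placebo+AIH and caffeine+SHAM. A dAIH-over-dSHAM ratio has caffeine in its denominator and, if the two dAIH conditions are pooled, in half of its numerator. Caffeine is the new element in this trial, yet the comparison that isolates it, caffeine+AIH with placebo+AIH, is not planned for the hypertension rate or for mmHg.

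At stake is what the trial can say about BP safety of the combination. Protocol 11a supports the safety of AIH by citing earlier findings of no change in mean arterial pressure. An event ratio alone cannot confirm or challenge a statement of that kind for caffeine plus AIH.

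**Working it through.** **Figures in the plan.** The documents give no BP mean, SD or power, so there is nothing to reproduce for BP. The only stated power (0.80 at N=20) is for the 10MWT and does not bear on this point. From the documents come the 140/90 cut, N=20 with 17% attrition (20 × 0.83 = 16.6, about 17 completers) and a two-sided 5% level (SAP 16). Everything else below is assumed.

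**Number of readings.** Protocol 11a gives 15 episodes per session. If each counts as one breathing interval, that is 15/5 = 3 readings, plus 2 around walking practice and 1 at session end: 6 per session and 30 over five sessions. The assumed 25 per round is therefore plausible. The scheduled readings in Protocol 18 (baseline, after session 5, two follow-ups) are only 4.

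**What the ratio estimates.** Suppose AIH multiplies the event rate by *a* and caffeine by *c*, with equal numbers of readings and the two dAIH conditions pooled. The ratio is then [(*ac* + *a*)/2]/*c* = *a*(1 + *c*)/(2*c*). This is below *a* whenever *c* > 1, so a caffeine effect on BP pulls the ratio down.

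**Power on mmHg.** Assume a 5 mmHg systolic shift, person-by-round SD 6 and reading SD 9. Stable differences between people cancel, so the SD of the paired difference in round means is √[2(6² + 9²/k)] for k readings.
- k = 25: √[2(36 + 3.24)] = 8.86. Noncentrality at n=20 is 5√20/8.86 = 2.52, power 67%. At n=17 it is 5√17/8.86 = 2.33, power 59%.
- k = 4, all shifted: √[2(36 + 20.25)] = 10.61. Noncentrality at n=20 is 2.11, power 52%.
- k = 4, one shifted: the mean moves 5/4 = 1.25 mmHg. Noncentrality is 1.25√20/10.61 = 0.53, power 8%.

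**Power on the event rate.** This was simulated with the same inputs, plus between-person systolic SD 12, usual systolic below 140 and a 3 mmHg diastolic shift. The test was a paired t-test on each person's rate of readings above 140/90. The two figures in the last column come from two different diastolic models (n=20).

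| Readings per round | Mean systolic | mmHg | Event rate |
|---|---|---|---|
| 25 | 110 | 66% | 12–15% |
| 25 | 118 | 68% | 29–39% |
| 25 | 126 | 66% | 44–50% |
| 4 | 110 | 52% | 5–8% |
| 4 | 118 | 50% | 15–21% |
| 4 | 126 | 49% | 28–31% |

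Over 36 scenarios (n=17 or 20, person-by-round SD 4–8) the gain ran from 8 points (39% v 31%) to 71 points (88% v 17%). With only one of four readings shifted it was about 8% v 2–6%.

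**A second set of assumptions.** Take 17 completers, no person-by-round term, within-person SD 8–12, mean 110–130, and a cut on systolic only. Eight readings and a 5 mmHg rise gave 89–100% v 4–75%. The loss all but disappeared with eight readings, mean 130, SD 8 and an 8 mmHg rise (100% v 99%).

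**Undefined ratio.** At mean 110, between-person SD 12 and within-person SD 8, a reading has SD √(144 + 64) = 14.4, and P(>140) = 1 − Φ(30/14.4) = 0.019. With one reading from each of 17 people, the chance of no control event is (1 − 0.019)^17 ≈ 0.72. With eight readings each it is 0.27 by simulation. With 25 readings and the first set of assumptions (systolic only) it falls to about 0.03, so an undefined ratio is a risk mainly when readings are few.

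**The case against.** A reader might infer that BP is compared only at 140/90. That is too broad: dysreflexia, partly defined by a 20 mmHg systolic rise from baseline, is compared as well. It is still a yes/no event that needs symptoms and a diagnosis, so it does not supply the missing contrast.

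A reader might also infer that the protocol calls it essential to detect any BP rise. It says onset of significant pathology, with hypertension as one example. An event rate answers that question directly, which is a good reason to keep it. An mmHg difference answers a different question.

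Nor would a rise below the cut be wholly hidden. Read literally, the promise of a change with a CI for all measures covers BP in mmHg. Three separate intervals are not a paired contrast, however, and they do not give the difference between conditions.

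The population may sit nearer the cut than the exclusion suggests, because Protocol 11d allows medication for systemic hypertension. The gap narrows at higher mean pressure but was still present at 126.

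The strongest objection is to the power figures, and much of it stands. The protocol names no test for the ratio, so the event-rate test is a construct of this check. That test is also conservative at low pressure: under no effect at mean 110 it rejected 1.6% of the time, against 6.1% for mmHg. Matching the test sizes changed 67% v 17% to 69% v 27%. The covariate-adjusted model proposed below was not simulated. The gain also depends on using readings taken while an effect could be present; on the four scheduled readings it nearly vanishes if only the session-5 reading moves.

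**Conclusion.** The point holds in a limited form. Every planned between-intervention comparison involving BP is an event rate, no mmHg contrast is specified, and the 140/90 ratio does not separate caffeine from AIH. These statements follow from the text and need no assumption.

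That the ratio is likely to be insensitive to a rise below the cut follows from excluding hypertension; by how much is not knowable from the documents. With an assumed 5 mmHg shift, 25 readings, person-by-round SD 6 and 17–20 people, power is about 59–67% on mmHg against 11–50% on the event rate. These figures show direction and range; they do not measure the plan's own power.

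The documents do not support going further and saying that the event rates are the wrong safety result, or that a null ratio would be reported as no BP effect.

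**What to change.** In Protocol 18 and SAP 27, keep the 140/90 and dysreflexia event rates as clinical safety results and add one analysis in mmHg:

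- For each person and round, average systolic and diastolic BP over the during- and post-session readings.
- Compare within person, adjusting for that round's pre-exposure BP; the SAP should name the reading used.
- Report two differences with 95% CIs: caffeine+AIH v caffeine+SHAM (effect of AIH) and caffeine+AIH v placebo+AIH (effect of caffeine).

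The cost is wording in both documents and one more safety model on data already collected, with no new measurement or burden on participants. A mean difference does not show who crossed a clinical limit, so the event counts must stay beside it. Readings lost when a session is stopped affect both scales and should be reported. The 140/90 threshold used for monitoring is not changed.
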